#### 9 STATISTICAL CONSIDERATIONS

## 9.1 General Design Issues

This is a Phase I/II, multi-center, open-label, non-comparative study to evaluate the safety, acceptability, tolerability, and pharmacokinetics of CAB and RPV (oral lead-in and injectable formulations). The primary goals of the study are to propose the weight band dosing of oral CAB + oral RPV followed by CAB LA + RPV LA in children two to less than 12 years of age living with HIV-1, and to describe participant choice and experience with the regimen with or without an oral lead-in period.

The study has two cohorts. Cohort 1 is designed to come up with a proposed a weight band dosing for oral CAB + RPV followed by CAB LA + RPV LA based primarily on PK, safety and tolerability data. Cohort 2 is designed to describe the preference between CAB + RPV (oral + injectable) and CAB LA + RPV LA (injectable) and participants and or their parents/caregivers when given a choice between the two treatments. Overall study data can also help inform possible implementation of the CAB + RPV regimens in children two to less than 12 years of age living with HIV-1.

In making dosing decisions, the team will review available data as described in Section 3. The details of the review of safety data during the dose-finding phase are described in this section.

This statistical section also describes the outcome measures and planned analyses for the study objectives on safety, tolerability, acceptability, virologic response and immunologic response. Please refer to Section 10 for all matters which deal with PK study objectives, including the definition of outcome measures and planned analyses.

A minimum of 50 participants will be enrolled to Cohort 1 and will receive CAB and RPV oral leadin followed by CAB LA + RPV LA. Up to 20-40 participants will be enrolled to Cohort 2 and will receive CAB LA + RPV LA with or without an optional oral lead-in of CAB and RPV. Safety data will be summarized for the cohorts and for the groups based on participant weight at entry and study drug dosing. The precision of the estimates will depend on the number of participants included in the safety analysis. It is recognized that Cohort 2 estimates of safety failures for children on CAB + RPV (oral + injectable) and CAB LA + RPV LA (injectable) may be less precise due to small sample size.

The analysis for the Primary Analysis Report will be performed when Cohort 1 complete data through Week 24 are available. Additional analysis reports for supporting regulatory submissions or publication (e.g., safety update, HTA-health technology assessment) and final reports which include data beyond Week 24 will be generated. The details of analyses for these reports will be specified in the Primary Statistical Analysis Plan (Primary SAP) and other study analysis planning documents.

The study is designed to allow changing the dose regimen as described in Section 5.1.2. The study also allows for the use of oral bridging during the injection phase. Analysis specifications related to any dose changes or the use of oral bridging are in Section 9.6. Additional specifications may be added in the Primary SAP.

Participants assigned or who opt to receive LA injectable regimen with oral lead-in of CAB and RPV, i.e., participants in Cohort 1 and 2a, may fail the Step 2 eligibility criteria and thus are not able to proceed with the injectable phase of the regimen. The Primary SAP will describe the analyses to address the safety objectives in case some Cohort 1 and 2a participants do not proceed with the injectable phase of the regimen.

#### 9.2 Outcome Measures and Estimands

The primary and secondary outcome measures listed in this section will be further described in the study's Primary SAP, which will define the contents of the final analysis reports.

The Safety Outcome Measures will consider the adverse event's severity (i.e., grade), seriousness (i.e., using ICH criteria for serious events), and attribution to the study drugs. The following specifications will also be used for the safety outcome measures and are referenced in Table 4:

- **Drug-related safety failure events** include the following:
  - o Grade 3 or higher adverse events assessed as related to study drug(s)
  - SAEs assessed as related to study drug(s)
  - Premature permanent discontinuation of study drug(s) due to an adverse event assessed as related to study drug(s)
- Adverse event attribution to the study drugs will be based on site's assessment.
- **HIV-1 Virologic Outcome Measures** based on HIV-1 RNA (copies/mL), will be calculated according to the US FDA-defined Snapshot Algorithm and will use 50 and 200 copies/mL as threshold with three main categories each.
  - o HIV-1 RNA <50 copies/mL, HIV-1 RNA ≥50 copies/mL, and no virologic data.
  - o HIV-1 RNA <200 copies/mL, HIV-1 RNA ≥200 copies/mL, and no virologic data.
- Confirmed virologic failure is defined in Section 8.3.

The primary objectives for Cohort 1 will be supported by the PK outcome measures and safety described in Section 10.2 and in the table below, respectively. As stated above, the PK-related study objectives will be supported by the PK outcome measures and planned analyses as described in Section 10.

Table 4.
Outcome Measures

	Outcome Measures	
9.2.1 Coho	rt 1 Primary Outcome Measures	
9.2.1.1	Safety of the CAB + RPV oral lead-in and 24 weeks of CAB + RPV (oral and injectable)	
	
 
Proportion of children who experience the following during the CAB + RPV oral lead-in period:         
 
drug-related safety failure event
 
grade 3 or higher adverse event
 
SAE
 
premature permanent discontinuation study treatment due to an adverse event
 
 
 
	
	
 
Proportion of children who experience the following during the 24 weeks of CAB + RPV (oral and injectable):         
 
drug-related safety failure event
 
grade 3 or higher adverse event
 
SAE
 
premature permanent discontinuation study treatment due to an adverse event
 
 
 
	
9.2.2 Coho 9.2.2.1	rt 1 Secondary Outcome Measures  Proportion of children who experience the following through Weeks 48	
3.2.2.1	and 72 of CAB + RPV (oral and injectable):  o drug-related safety failure event o grade 3 or higher adverse event o SAE o premature permanent discontinuation study treatment due to an adverse event	
9.2.2.2	
 
Proportion of children who have HIV-1 RNA <50 and ≥50, copies/ml at Weeks 24, 48, and 72 using the FDA Snapshot algorithm
 
Proportion of children who have HIV-1 RNA <200 and ≥200 copies/ml at Weeks 24, 48, and 72 using the FDA Snapshot algorithm
 
Proportion of children with confirmed virologic failure at Weeks 24, 48 and 72 while on CAB + RPV
 
	
9.2.2.3	Tolerability: Child and/or parent/caregiver responses to questionnaires about CAB or RPV side effects, pain associated with injections, and injection site reactions at Weeks 24, 48, and 72.  Acceptability: Child and/or parent/caregiver reported attitudes about CAB or RPV, including willingness to use at Weeks 24, 48, and 72.	
9.2.2.4	Proportion for each group based on genotypic and phenotypic resistance to CAB or RPV for children who experience virologic failure while on CAB + RPV.	

9.2.2.5	Median for CD4 count and percentage at Weeks 24, 48 and 72.		
	Median change from baseline CD4 count and percentage at Weeks 24, 48 and 72.		
9.2.3 Coho	ort 2 Secondary Outcome Measures		
9.2.3.1	For children who are on 48 weeks of CAB + RPV (oral and injectable) OR 44 weeks of CAB LA + RPV LA (injectable):  Tolerability: Child and/or parent/caregiver responses to questionnaires about CAB or RPV side effects, pain associated with injections, and injection site reactions		
	Acceptability: Child and/or parent/caregiver reported attitudes about CAB or RPV, including willingness to use		
9.2.3.2	Safety of 48 weeks of CAB + RPV (oral and injectable) OR 44 weeks of CAB LA + RPV LA (injectable)		
	Proportion of children who experience the following during the 48 weeks of CAB + RPV (oral and injectable) OR the 44 weeks of CAB LA + RPV LA (injectable):  o drug-related safety failure event o grade 3 or higher adverse event SAE o premature permanent discontinuation study treatment due to an		
	adverse event		
9.2.3.3	For children who are on 48 weeks of CAB + RPV (oral and injectable) OR 44 weeks of CAB LA + RPV LA (injectable):  Maintenance of virologic suppression  ○ Proportion of children who have HIV-1 RNA <50 and ≥50, copies/ml using the FDA Snapshot algorithm  ○ Proportion of children who have HIV-1 RNA <200 and ≥200 copies/ml using the FDA Snapshot algorithm  ○ Proportion of children with confirmed virologic failure while on treatment		
	
 
Immunologic activity:
 
Median and Interquartile Range for CD4 count and percentage
 
Median and Interquartile Range change from baseline CD4 count and percentage
 
		
9.2.3.4	Proportion for each group based on genotypic and phenotypic resistance to CAB and RPV for children who experience virologic failure while on 48 weeks of CAB + RPV (oral and injectable) OR while on 44 weeks of CAB LA + RPV LA (injectable).		
9.2.4 Othe	r Outcome Measures		

9.2.4.1	Proportion of children who experience the following through 48 weeks		
	following permanent discontinuation of CAB LA + RPV LA:		
	o drug-related safety failure event		
	o grade 3 or higher adverse event		
	o SAE		

Table 4 shows the specifications for the estimands related to the primary safety outcome measures listed above. Additional details, including additional intercurrent events (e.g., death) for the primary safety outcome measures may be specified in the Primary SAP. Estimands related to the outcome measures for the secondary and other objectives will be included in the Primary SAP.

Table 5. Safety Estimands

	Primary Safety Estimands			
	Cohort 1	Cohort 1		
	(through week 4)	(through week 24)		
A primary	What is the safety profile of ~4	What is the safety profile of		
question of	weeks of oral CAB+RPV in	CAB+RPV (~4 weeks of oral lead-in		
interest	virologically suppressed children	followed by ~20 weeks of injectable)		
	living with HIV-1, two to less	in virologically suppressed children		
	than 12 years of age?	living with HIV-1, two to less than		
A 44 *17 4		12 years of age?		
Attributes				
Population	Virologically suppressed children liv	ving with HIV, two to less than 12		
	years of age			
Endpoints/ Variables	Through week 4	Through week 24		
variables	o Drug-related safety	failure event		
	o Grade 3 or higher a	ndverse event		
	o SAE			
	o Permanent discontinuation of study treatment due to an			
	adverse event			
Treatment	Oral CAB + Oral RPV once daily	Oral CAB + Oral RPV once daily		
condition	through Week 4 (see Schema on	through Week 4, followed by LA		
	treatment details)	CAB + LA RPV Q4W or Q8W		
		through Week 24 (see Schema on		
Intercurrent	Duama atuma na mma an ant	treatment details)		
events (ICE)	Premature permanent discontinuation of study drugs for	Premature permanent discontinuation of study drugs for		
events (ICE)	any reasons through week 4 has	any reasons through Week 24 has		
	impact on safety assessment.	impact on safety assessment. While-		
	While-on-treatment strategy will	on-treatment strategy will be applied		
	be applied to address this ICE.	to address this ICE.		
	Other analysis approaches may also be explored to address missing			
	values due to premature permanent discontinuation as a part of sensitivity			
	analysis. Details will be described in the Statistical Analysis Plan (SAP).			
Population-	Proportions of children experiencing the safety outcome measures and			
level summary	their two-sided 95% confidence interval			

#### 9.3 Randomization and Stratification

There will be no randomization for the study. Participants will be stratified into weight bands based on their weight at study entry (Weight Band 1 25-34.9 kg, Weight Band 2 35-<40 kg Weight Band 3 20-24.9 kg, Weight Band 4 14-19.9 kg, and Weight Band 5 10-13.9 kg). Cohort 1 has accrual requirements per weight band as well as across Weight Bands 1 and 2 and across Weight Bands 3, 4, and 5, as described in Section 3. There are no weight band accrual requirements in Cohort 2, although there are accrual requirements for Cohort 2a and Cohort 2b, as described in Section 3.

# 9.4 Sample Size and Accrual

Up to 90 children will be enrolled across Cohorts 1 and 2. Cohort 1 will enroll up to 70 participants in order to achieve at least 50 evaluable participants. Cohort 2 will open to accrual once accrual to Cohort 1 is complete and results on Week 12 interim analyses are available. Additional specifications on weight-band accrual targets (both per weight band and across weight bands) are specified in Section 3.1. Sample size specifications of parents/caregivers of child participants for the behavioral assessments and qualitative in-depth interviews to assess study drug acceptability and tolerability are in Sections 3.1 and 3.4. The sample size requirements are primarily driven by consideration for main analyses for the safety study objectives. For example, for the 50 participants included in Cohort 1 primary safety analysis, if 2 (4%) experience a safety failure event as defined in Section 9.2, the 95% Clopper-Pearson Confidence Interval would be 0-14% (please see Table 6), which provides sufficient precision to exclude a rate ≥ 15% based on the upper limit of CI. Moreover, of the 50 Cohort 1 participants included in the primary safety analysis, the probability of observing at least one participant who experiences such an event is high (87%). assuming a true rate of the safety failure event in the study population of 4% (please see Table 8).

General specifications for the analysis of safety data are in Section 9.6. To assess the safety of the study drugs, point and 95% Clopper-Pearson Confidence Interval (CI) estimates of proportion of participants who experience at least one safety failure event of interest for a defined safety outcome measure while on CAB+RPV will be generated. Note that the safety failure events of interest will be specific to a safety outcome measure as defined in Section 9.2. Table 6 shows the precision of the 95% CI estimates under different assumptions on sample size and number of safety failures. It shows the precision of the estimates for the main safety analyses, i.e. for a potential of 18 or 32 participants who might contribute data to the per analysis group estimates based on weight at entry (e.g. pooled across Weight Bands 1 and 2, pooled across Weight Bands 3, 4 and 5); and for a potential minimum of 50 and maximum of 70 participants who might contribute data to the overall estimate for Cohort 1 (i.e., pooled across all 5 weight bands), under the likely scenarios that at most 25%-30% of the participants are safety failures and if 50% of the participants are safety failures, as this corresponds to when the confidence interval will be the widest. It also shows the precision of the estimate for a potential of 6 or 10 participants who might contribute to the per weight band estimates, i.e., additional analyses specified in Section 9.6. The table indicates that the 95% CI estimates will be quite wide around the sample size of 6 participants in a Cohort 1 weight band but will be considerably narrower around the target sample size of 50 participants in Cohort 1.

Table 7 shows the point and 95% CI estimates for potential of 20 participants in Cohort 2 overall safety analysis; and potential 5 or 10 participants in Cohorts 2a and 2b safety analyses.

Table 6.
95% Confidence Intervals around Potential Proportions of Cohort 1 Participants Classified as Safety Failures

	Failures			
Number of Participants	Number of Safety Failures	Proportion of Safety Failures a		
6	0	0.00 (0.00, 0.46)		
	1	0.17 (0.00, 0.64)		
	2	0.33 (0.04, 0.78)		
	3	0.50 (0.12, 0.88)		
10	0	0.00 (0.00, 0.31)		
	1	0.10 (0.00, 0.45)		
	2	0.20 (0.03, 0.56)		
	3	0.30 (0.07, 0.65)		
	5	0.50 (0.19, 0.81)		
18	0	0.00 (0.00, 0.19)		
	1	0.06 (0.00, 0.27)		
	2	0.11 (0.01, 0.35)		
	3	0.17 (0.04, 0.41)		
	4	0.22 (0.06, 0.48)		
	5	0.28 (0.10, 0.53)		
	6	0.33 (0.13, 0.59)		
	9	0.50 (0.26, 0.74)		
32	0	0.00 (0.00, 0.11)		
	1	0.03 (0.00, 0.16)		
	2	0.06 (0.01, 0.21)		
	3	0.09 (0.02, 0.25)		
	5	0.16 (0.05, 0.33)		
	8	0.25 (0.11, 0.43)		
	11	0.34 (0.19, 0.53)		
	16	0.50 (0.32, 0.68)		
50	0	0.00 (0.00, 0.07)		
	1	0.02 (0.00, 0.11)		
	2	0.04 (0.00, 0.14)		
	4	0.08 (0.02, 0.19)		
	6	0.12 (0.05, 0.24)		
	9	0.18 (0.09, 0.31)		
	12	0.24 (0.13, 0.38)		
	15	0.30 (0.18, 0.45)		
	1			

Number of Participants	Number of Safety Failures	Proportion of Safety Failures a
	25	0.50 (0.36, 0.64)
70	0	0.00 (0.00, 0.05)
	1	0.01 (0.00, 0.08)
	2	0.03 (0.00, 0.10)
	3	0.04 (0.01, 0.12)
	5	0.07 (0.02, 0.16)
	35	0.50 (0.38, 0.62)

<sup>a Clopper-Pearson exact confidence interval estimates using SAS Version 9.4.

Table 7.
95% Confidence Intervals around Potential Proportions of Cohort 2 Participants Classified as Safety
Failures

Failures					
Number of Participants	Number of Safety Failures	Proportion of Safety Failures a			
4	0	0.00 (0.00, 0.60)			
	1	0.25 (0.01, 0.81)			
	2	0.50 (0.07, 0.93)			
10	0	0.00 (0.00, 0.31)			
	1	0.10 (0.00, 0.45)			
	2	0.20 (0.03, 0.56)			
	3	0.30 (0.07, 0.65)			
	5	0.50 (0.19, 0.81)			
20	0	0.00 (0.00, 0.17)			
	1	0.05 (0.00, 0.25)			
	2	0.10 (0.01, 0.32)			
	3	0.15 (0.03, 0.38)			
	4	0.20 (0.06, 0.44)			
	5	0.25 (0.09, 0.49)			
	10	0.50 (0.27, 0.73)			

<sup>a Clopper-Pearson exact confidence interval estimates using SAS Version 9.4.

Table 8 provides the binomial probabilities of observing at least one participant with a safety failure event of interest for a range of Cohort 1 sample sizes and a range of true proportions of children with at least one safety failure event of interest. For example, if the true proportion of children who will experience at least one safety failure event of interest while on CAB + RPV is 5%, the probability of having at least one participant experiencing such event in the study out of 15 and 50 participants are 54% and 92%, respectively.

Table 8.

Probability that at least one Cohort 1 participant will experience at least one safety failure event under different assumptions.

True proportion of children who are safety	Sample Size (N)						
failures	5	10	15	20	35	50	70
0.01	0.05	0.10	0.14	0.18	0.30	0.39	0.51
0.02	0.10	0.18	0.26	0.33	0.51	0.64	0.76
0.03	0.14	0.26	0.37	0.46	0.66	0.78	0.88
0.04	0.18	0.34	0.46	0.56	0.76	0.87	0.94
0.05	0.23	0.40	0.54	0.64	0.83	0.92	0.97
0.06	0.27	0.46	0.60	0.71	0.89	0.95	0.99
0.07	0.30	0.52	0.66	0.77	0.92	0.97	0.99
0.08	0.34	0.57	0.71	0.81	0.95	0.98	>0.99
0.09	0.38	0.61	0.76	0.85	0.96	0.99	>0.99
0.10	0.41	0.65	0.79	0.88	0.97	0.99	>0.99

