# 3 STUDY DESIGN

#### 3.1 Overview

This is a Phase I/II, multicenter, open-label, non-comparative study to evaluate the safety, tolerability, acceptability, and PK of oral CAB and oral RPV followed by long-acting injectable CAB (CAB LA) and long-acting injectable RPV (RPV LA) to propose the weight-band dosing in virologically suppressed children living with HIV-1 aged two to less than 12 years. The study will also assess the long-acting injectable regimen with and without an oral lead-in period in the same study population.

This study will be conducted among up to 90 children weighing ≥10 kgs and <40 kgs, who are virologically suppressed on stable ART. Approximately 90 parents/caregivers of child participants will also enroll to complete tolerability and acceptability assessments (see Section 6.15). In-depth qualitative interviews with a subset of enrolled parents/caregivers will also be conducted as described in Section 3.4. Unless otherwise noted, the term 'participant' will refer to the children enrolled in the study.

Refer to Section 4 for the study eligibility criteria for participants and caregivers, as well as a description of the study recruitment, screening, and enrollment process. Participants and caregivers will be enrolled at selected study sites.

The study will include two discrete cohorts.

Cohort 1 will open to accrual first. In Cohort 1, participants will be enrolled across five weights bands as follows: Weight Band 1 (35-<40kg), Weight Band 2 (25-34.9kg), Weight Band 3 (20-24.9kg), Weight Band 4 (14-19.9kg), and Weight Band 5 (10-13.9kg).

At least 50 evaluable participants (defined in Section 3.2) will be enrolled in Cohort 1. At least 18 evaluable participants will enroll across Weight Bands 1 and 2 and at least 32 evaluable participants will enroll across Weight Bands 3, 4, and 5. Additionally, at least 6 evaluable participants will be enrolled in each of the four highest weight bands (Weight Bands 1, 2, 3, and 4). At least 10 evaluable participants will be enrolled in the lowest weight band (Weight Band 5).

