# 5.1 Study Product Regimen

At Entry, all participants will discontinue their pre-study cART regimen and will be assigned to a dosing regimen based on their weight at entry to the applicable cohort. Weight-based dose adjustments will made according to guidance provided in Section 5.1.1 below. Dosing regimens may be modified following the Cohort 1 interim analyses or based on experience in the study, in which case, the new regimen will be specified per Section 5.1.2 below.

Cohort 1 participants will receive oral CAB + oral RPV followed by intramuscular CAB LA + RPV LA as shown in Table 1 (for oral dosing) and Table 2 (for LA injections).

Cohort 2a participants will receive oral CAB + oral RPV followed by intramuscular CAB LA + RPV LA. Cohort 2b participants will receive intramuscular CAB LA + RPV LA only. As described in Section 3, Cohort 2a and Cohort 2b will be opened to accrual following the Cohort 1 interim analyses and full accrual of Cohort 1. The oral and injectable dosing regimens for both Cohort 2a and Cohort 2b will also be communicated, per weight band, at that time; see Section 5.1.2 below.

Table 1.
Cohort 1: Initial Oral Lead-In Dosing Regimen

Weight Band	Daily Oral Dose (through the Week 4b visit)
Weight Band 1 35-<40 kg	30mg CAB + 25mg RPV  • Administered as one 30mg CAB tablet + one 25mg RPV tablet
Weight Band 2 25-34.9 kg	10mg CAB + 25mg RPV  • Administered as two 5mg CAB DT + one 25mg RPV tablet
Weight Band 3 20-24.9 kg	10mg CAB + 15mg RPV  ◆ Administered as two 5mg CAB DT + six 2.5mg RPV tablets
Weight Band 4 14-19.9 kg	10mg CAB + 12.5mg RPV  ◆ Administered as two 5mg CAB DT + five 2.5mg RPV tablets
Weight Band 5 10-13.9 kg	10mg CAB + 12.5mg RPV  ◆ Administered as two 5mg CAB DT + five 2.5mg RPV tablets

Table 2.
Cohort 1: Initial (Q4W) IM Injection Dosing Regimen

Confort 1. Initial (4444) in injection bosing Kegimen		
Weight Band	Q4W Long-acting IM Dose Regimen	
Weight Band 1	Initial injections (Wk 4b): 600mg CAB LA + 900mg RPV LA	
35-<40 kg	Subsequent injections (following Wk 4b), every four weeks: 400mg CAB LA + 600mg RPV LA	
	Initial injections (Wk 4b): 300mg CAB LA + 600mg RPV LA	
Weight Band 2 25-34.9 kg	Subsequent injections (following Wk 4b), every four weeks: 200mg CAB LA + 450mg RPV LA	
Weight Band 3 20-24.9 kg	Initial injections (Wk 4b): 300mg CAB LA + 600mg RPV LA	
20 24.7 kg	Subsequent injections (following Wk 4b), every four weeks: 200mg CAB LA + 450mg RPV LA	

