#### Analysis of Safety and Tolerability Data:

The population of interest for the safety and tolerability analyses are virologically suppressed children living with HIV, two to less than 12 years of age, who received oral CAB + RPV (oral and injectable). Other analysis populations of interest, e.g., children on recommended dose population, may be added and specifications will be included in the Primary SAP.

Separate analyses will be done for each of the safety outcome measures. In addition to the analyses of the safety outcome measures, the proportion of participants who have injection site adverse events, adverse events related to study procedure (e.g., injection site reactions), and any grade adverse event related to the study drug(s) will be provided.

Summaries of worst grade adverse events by MedDRA Preferred Term (PT) grouped by System Organ Class SOC will be generated for: (i) all adverse events, and (ii) all adverse events assessed by site as related to the study drug(s).

Cohorts 1 and 2 analysis groups will be based on weight at entry (i.e., pooled data across Weight Bands 1 and 2; and pooled data across Weight Bands 3, 4 and 5) and study drug dose for the oral lead-in and/or at start of the injectable phase. The main safety analysis will include estimates overall and per analysis group. As additional analysis, per weight band estimates will be provided recognizing that due to small sample size these estimates will be less precise.

Analysis of Virology, Immunology, Phenotypic and Genotypic Resistance Data: The population of interest for the analyses of virology and immunology data are virologically suppressed children living with HIV, 2 to less than 12 years of age, who received oral CAB + RPV (oral and injectable).

The population of interest for the analysis of phenotypic and genotypic resistance data are the virologically suppressed children living with HIV, 2 to less than 12 years of age, who received oral CAB + RPV (oral and injectable) and are confirmed virologic failure while on CAB + RPV. Cohort 1 and 2 analysis groups will be based on study drug dose for the oral lead-in and/or at start of the injectable phase.

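### Section 9.4 gives main per-group safety precision for 18 and 32 children grouped by weight alone, but Sections 9.1 and 9.6 form the main groups by weight and dose, which are smaller

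*Protocol*

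**What the plan says.** Section 9.4 describes Table 6 as showing interval width for the main safety analyses "for a potential of 18 or 32 participants who might contribute data to the per analysis group estimates based on weight at entry". The two groups are Weight Bands 1–2 and Weight Bands 3–5. The smallest sample sizes are assigned to a different, additional analysis: "It also shows the precision of the estimate for a potential of 6 or 10 participants who might contribute to the per weight band estimates".

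Section 9.6 (Analysis of Safety and Tolerability Data) defines the groups differently. It takes the same two weight pools and adds a second factor: "and study drug dose for the oral lead-in and/or at start of the injectable phase". It then makes these groups part of the main analysis: "The main safety analysis will include estimates overall and per analysis group". Section 9.1 agrees with 9.6: "Safety data will be summarized for the cohorts and for the groups based on participant weight at entry and study drug dosing". The per-group intervals in 9.6.1.1 and 9.6.1.2 are the ones affected.

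The accrual targets in Section 3.1 are counted by weight band, not by dose. For example, "At least 18 evaluable participants will enroll across Weight Bands 1 and 2". Bands 3–5 need at least 32 evaluable children. The band minima are 6 in each of Bands 1–4 and 10 in Band 5.

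**The concern.** The sections do not describe the same analysis. In Tables 1 and 2 of Section 5.1, Band 1 differs from Band 2 in both oral and injected starting dose, and Band 3 differs from Bands 4–5 in both. Only Band 1, for instance, starts with "Initial injections (Wk 4b): 600mg CAB LA + 900mg RPV LA". If dose is a grouping factor, neither 18 nor 32 is the size of a main analysis group, even before any dose is changed.

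The design also allows doses to change. Newly enrolled children then start on the new dose (Section 3.2), and nothing in the protocol fixes how many must start on either dose.

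At stake is what a reader may expect of the per-group intervals. The trial is meant to propose dosing by weight band, and these intervals are the main safety summary below the overall figure. Section 9.4 promises them a precision that the grouping in 9.6 will not deliver.

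**Working it through.** **Method.** Table 6 uses two-sided 95% Clopper-Pearson intervals. With 0 events in n, the upper limit is 1 − 0.025^(1/n).

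**The plan's own figures.**
- n = 18: 1 − 0.025^(1/18) = 0.185, printed as 0.19.
- n = 32: 1 − 0.025^(1/32) = 0.109, printed as 0.11.
- All 40 rows of Table 6 reproduce to two decimals. So does the 87% chance of at least one event in 50 at a true rate of 4% (1 − 0.96^50 = 0.870).

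The arithmetic is correct. The question is which group sizes it should be applied to.

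**Starting doses (Section 5.1) and minima (Section 3.1).**

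| Weight pool | Band | Oral CAB + RPV, mg | First injection CAB LA + RPV LA, mg | Minimum evaluable |
|---|---|---|---|---|
| 1–2 | 1 | 30 + 25 | 600 + 900 | 6 |
| 1–2 | 2 | 10 + 25 | 300 + 600 | 6 |
| 3–5 | 3 | 10 + 15 | 300 + 600 | 6 |
| 3–5 | 4 | 10 + 12.5 | 300 + 450 | 6 |
| 3–5 | 5 | 10 + 12.5 | 300 + 450 | 10 |

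Crossing weight pool with dose gives four groups: Band 1, Band 2, Band 3, and Bands 4–5. The result is the same by oral dose, by first injection, or by both. Bands 2 and 3 share a first injection but lie in different weight pools.

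**Bands 1–2 at exactly 18.** Each band has at least 6, so the split runs from 6 and 12 to 9 and 9. The smaller group has at most 9.
- 0/6: 1 − 0.025^(1/6) = 0.459
- 0/9: 1 − 0.025^(1/9) = 0.336
- 0/12: 1 − 0.025^(1/12) = 0.265

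The smaller group's upper limit is therefore 34% to 46%, against the 19% shown for 18. With one event the upper limit is 64% at n = 6, against 27% at n = 18.

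**Bands 3–5 at exactly 32.** Band 3 has at least 6, and Bands 4–5 have at least 6 + 10 = 16. The split runs from 6 and 26 to 16 and 16.
- 6 and 26: 0/6 gives 0.459; 0/26 gives 1 − 0.025^(1/26) = 0.132.
- 16 and 16: 0/16 gives 1 − 0.025^(1/16) = 0.206 in each.

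The limits are 46% and 13%, or 21% and 21%, against the 11% shown for 32.

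**Chance of seeing at least one event at a true rate of 4%,** 1 − 0.96^n: 22% at n = 6, 48% at 16, 52% at 18 and 73% at 32.

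**After a dose modification.** The dose-evaluable definition in Section 3.2 requires treatment on the dose being evaluated; the evaluable definition does not. The targets of 18 and 32 count evaluable children whatever dose they started on. Neither 3.2 nor 5.1.2 sets a new minimum. The guaranteed number starting on either the old or the new dose is therefore 0.

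**The case against.** The best counter-argument is that dose in 9.6 need not mean milligrams. The same sentence explicitly pools Bands 1 and 2, which never share a starting dose, and a milligram split would nearly duplicate the per-band estimates that 9.6 labels additional. If dose means initial versus modified regimen, both statements make sense, and 18 and 32 hold at the starting doses. This is a fair reading, but 9.6 does not state it. Even then, 18 and 32 hold only until a modification, for which the protocol makes explicit provision.

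Other points stand and limit the finding:

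- A reader might infer four groups of 6, 6, 6 and 16 together. Those sum to 34 and cannot occur with totals of at least 18 and 32. Each is a separate minimum.
- A reader might infer that no child would be studied on a modified dose. The 0 is a floor for children starting on it, not an expected size. Section 5.1.2 also moves current participants to the updated regimen.
- A reader might infer that every regimen change splits the groups. The factor in 9.6 is dose at oral lead-in and/or at the start of injections, so moving a child already receiving injections from Q4W to Q8W does not change the group.
- Section 9.4 is hedged, and Table 6 prints n = 6 and n = 10. The wide intervals are visible, but are attributed only to the per-band estimates.
- The safety set is All Treated, so actual counts may exceed the evaluable minima.
- These are descriptive intervals with no decision rule attached. The interim safety rule is in 9.5.2.

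**Conclusion.** The inconsistency is real and should be corrected. On the literal reading, with accrual exactly at the pooled minima, the smaller dose group in Bands 1–2 has an upper limit with no events of 34% to 46% rather than 19%. In Bands 3–5 the smaller group's limit is 21% to 46% rather than 11%. On the initial-versus-modified reading there is no discrepancy until a modification, and no guaranteed size afterwards.

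The figures assume evaluable counts at the Section 3.1 minima. For grouping by dose at the start of injections, they also assume that every child enters Step 2 and that none moves up a weight band during the lead-in; otherwise a group could fall below 6.

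This does not show that the trial is too small. The only explicit sufficiency claims in 9.4 are for 50 children: excluding a rate of 15% or more with 2 events, and the 87% chance of seeing an event. Both are unaffected. The 18 and 32 rows illustrate precision; they are not a formal sizing claim for each dose group.

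**What to change.** Reconcile 9.1, 9.4 and 9.6.

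- In 9.4, state that the 18 and 32 rows apply only when each weight group is pooled across doses. Add that the main weight-by-dose groups will be smaller: as few as 6 at the starting doses if dose means milligrams, and with no guaranteed minimum after a modification. Refer to the corresponding wider intervals. Give examples that respect the pooled totals, such as 6 and 12 or 9 and 9 for Bands 1–2, and 6 and 26 or 16 and 16 for Bands 3–5.
- In 9.6, say whether study drug dose means the milligram dose or initial versus modified regimen, and use the same wording in 9.1.

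It would also be possible to make the weight-only groups the main analysis and the dose split additional. That is debatable in a dose-finding trial, because the main estimate would then mix doses, and it is not needed to correct the stated precision.

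The cost is a few sentences and no additional children. The stated per-group precision becomes less favourable.
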